## 11.0 TOXICITIES/SIDE EFFECTS

### 11.1 Nivolumab and Ipilimumab toxicity overview

Nivolumab and Ipilimumab are currently in clinical development and both have been FDA-approved for use as monotherapies respectively. The entire safety profile of nivolumab plus ipilimumab is not known at this time. Measures will be taken to ensure the safety of the patients participating in this trial, including the use of stringent inclusion and exclusion criteria and close monitoring. Toxicity grading will be performed in accordance with NCI CTCAE 4.0. If toxicities are encountered, adjustments will be made to the study treatment as detailed in the sections below. All AEs and SAEs will be recorded during the trial and for up to 100 days after the last dose of study treatment.

### 11.2 Risks associated with nivolumab

#### **Likely**

- Fatigue
- Skin changes including: rash, itching, hives, dry skin, or redness
- Diarrhea
- Nausea
- Abdominal pain
- Decreased appetite
- Low red blood cells
- Joint pain or stiffness

#### **Less Likely**

- Bowel inflammation
- Liver function blood test abnormalities
- Loss of color (pigment) from areas of skin
- Dry mouth
- Vomiting
- Weight loss
- Thyroid gland abnormalities
- Blood chemistry abnormalities, including low blood phosphate, magnesium, and potassium levels.
- High blood uric acid level
- Lung inflammation
- Cough
- Dizziness
- Headache
- Low white blood cell
- Chills
- Muscle soreness, weakness, stiffness, spasms, or paralysis
- Pain in arms or legs
- Tingling, burning, or numbness in hands and feet
- Shortness of breath
- Abnormal taste
- Flushing
- High or low blood pressure
- Allergic reaction during or between study drug infusions
- Increased sensitivity of skin to sunlight
- Constipation
- Difficulty swallowing
- Heartburn
- Low blood platelets (may increase risk of bleeding)

**Rare but serious**

- Low blood oxygen level
- Acute lung injury or failure
- Collection of fluid around the lungs
- Inflammation of the appendix
- Increase in inflammatory blood proteins (e.g., lipase)
- Adrenal gland abnormalities
- Pituitary gland inflammation
- Changes in vision, inflammation of the eye (or optic nerve), or bleeding into the eye
- Swelling of the optic disc
- Liver inflammation
- Acute kidney injury or failure

- Inflammation of the mouth and lining of the digestive tract
- Swelling of the face, arms, or legs
- Inflammation of the pancreas
- Back pain
- Autoimmune disorders, including Guillain-Barre syndrome (associated with progressive muscle weakness or paralysis)
- Chest discomfort
- Heart palpitations
- Inflammation of the heart or its lining
- Collection of fluid around the heart
- Increased blood sugar
- Dehydration
- Infections: including sepsis, lung infections, and skin infections
- Decreased movement of the intestines
- Confusion
- Inflammation of the optic nerve
- Inflammation or loss of the lining of the brain and spinal cord
- Abnormal brain function due to brain inflammation
- Drug reaction with rash, blood cell abnormalities, enlarged lymph nodes, and internal organ involvement (including liver, kidney, and lung)
- Myasthenia gravis, a nerve disease that may cause weakness of eye, face, breathing, and swallowing muscles
- Muscle breakdown or inflammation in the muscle
- Toxic epidermal necrolysis, a potentially fatal disease characterized by blistering and peeling of the top layer of the skin resembling a severe burn, has occurred in patients who received nivolumab treatment
- Rhabdomyolysis (muscle fiber released into the blood stream which could damage your kidney) and polymyolysis (chronic inflammation with muscle weakness) has been reported in one patient
- Lung inflammation (pneumonitis)
- Death

### 11.2 Risks associated with ipilimumab

#### **Likely**

- Fever
- Nausea and/or vomiting
- Rash
- Diarrhea
- Inflammation of the colon
- Increased liver enzymes
- Fatigue

- Skin itchiness
- Decreased appetite
- Abdominal pain
- Headache
- Constipation
- Adrenal gland abnormalities
- Pituitary gland abnormalities
- Colitis

Most of the side effects are mild and may be treated with common medications.

### **Less Likely**

- Chills
- Weakness
- Muscle pain
- Redness of skin

### **Rare but Serious**

- Decrease in hormones of pituitary gland
- Allergic reactions
- Inflammation of the liver
- Inflammation of the pituitary gland
- Decreased red blood cells
- Loss of color from areas of skin
- Decreased or blurry vision, or inflammation of the eye
- Numbness or tingling
- Inflammation of the membrane surrounding the spinal cord and brain
- Inflammation of the kidneys
- Joint pain
- Death

## **11.3 Risks associated with Nivolumab and Ipilimumab Combined Therapy**

### **Likely. Some May Be Serious**

- Fatigue
- Fever and/or chills
- Flu-like feeling
- Skin changes including dryness, rash, or itching
- Vitiligo (loss of pigment or color in the skin)
- Diarrhea
- Nausea and/or vomiting
- Abdominal Pain

- Bowel Inflammation
- Dry Mouth
- Liver function blood test abnormalities
- Cough
- Shortness of breath
- Headache
- Dizziness
- Lung inflammation (pneumonitis)
- Joint pain or stiffness
- Decreased appetite
- Low blood pressure
- Inflammation of the thyroid
- Muscle soreness, weakness, stiffness, or spasms
- Increase in inflammatory blood proteins (e.g. lipase)

**Lung Inflammation:** It is possible that nivolumab may cause inflammation of the tissues of the lung. This adverse effect has been reported in approximately 3% of patients treated with nivolumab. Although many patients have no symptoms from this lung inflammation, some patients have developed mild to severe symptoms and 2 patients have died as a result of their lung inflammation. Symptoms of lung inflammation may include difficulty breathing, fever, or fatigue. Your doctor and nurse will watch you closely for signs that might show you are developing lung inflammation.

**Please inform your doctor or nurse at once if you experience any of the following:**

- Any new or increased shortness of breath
- Any new or increased chest pain
- Any new or increased cough or any significant change in your type of cough
- Any increase in the amount of supplemental oxygen you require
- Any fever, fatigue, or other symptoms that occur at the same time as changes to your breathing or other lung symptoms.

If you start to develop symptoms concerning for lung inflammation, your doctor will ask you to return to clinic to perform regular tests including physical exams, measurement of oxygen levels, pulmonary function tests, blood tests, bronchoscopy, and/or CT scans. This may require treatment with steroids or other immune suppressive medicines as well as holding nivolumab. You may even require hospitalization.

**Kidney inflammation:** It is possible that nivolumab may cause kidney damage due to inflammation in the kidneys. This is very rare. You should let your doctor know if you notice any decreased amount of urine, difficulty urinating, sudden weight gain, increased tiredness, increased thirst or inability to tolerate liquids. This may require treatment with steroids and holding nivolumab.

### **Reproductive risks**

Patients should not become pregnant or father a baby while on this study because the drugs in this study can affect an unborn baby. Women should not breastfeed a baby while on this study. It is important you understand that you need to use birth control while on this study.

### 11.3 Management Algorithms for Unique Nivolumab/Ipilimumab-Related Toxicities

Nivolumab and Ipilimumab are associated with AEs that can differ in severity and duration than AEs caused by other therapeutic classes. Early recognition and management of AEs associated with immuno-oncology agents may mitigate severe toxicity. Management Algorithms have been developed to assist investigators in assessing and managing the following groups of AEs:

- Gastrointestinal
- Renal
- Pulmonary
- Hepatic
- Endocrinopathy
- Skin
- Neurological

The above algorithms are found in appendix 1-7 or in the current Investigator Brochure.

### 11.4 Management of Nivolumab or Ipilimumab-Related Infusion Reactions

Since nivolumab and ipilimumab contain only human immunoglobulin protein sequences, it is unlikely to be immunogenic and induce infusion or hypersensitivity reactions. However, if such a reaction were to occur, it might manifest with fever, chills, rigors, headache, rash, pruritus, arthralgias, hypotension, hypertension, bronchospasm, or other allergic-like reactions.

Infusion reactions should be graded according to NCI CTCAE (Version 4.0) guidelines.

Treatment recommendations are provided below and may be modified as appropriate:

- For **Grade 1** symptoms: (mild reaction; infusion interruption not indicated; intervention not indicated):
  - Remain at bedside and monitor subject until recovery from symptoms. The following prophylactic premedications are recommended for future infusions: diphenhydramine 50 mg (or equivalent) and/or acetaminophen/paracetamol 325 to 1000 mg at least 30 minutes before additional nivolumab administrations.
- For **Grade 2** symptoms: (moderate reaction required therapy or infusion interruption but responds promptly to symptomatic treatment (e.g., antihistamines, non-steroidal anti-inflammatory drugs, narcotics, corticosteroids, bronchodilators, IV fluids); prophylactic medications indicated for ≤ 24 hours):
  - Stop infusion, begin an IV infusion of normal saline, and treat the subject with diphenhydramine 50 mg IV (or equivalent) and/or acetaminophen/paracetamol 325 to 1000 mg; remain at bedside and monitor subject until resolution of symptoms. Corticosteroid and/or bronchodilator therapy may also be administered as

appropriate. If the infusion is interrupted, then restart the infusion at 50% of the original infusion rate when symptoms resolve; if no further complications ensue after 30 minutes, the rate may be increased to 100% of the original infusion rate. Monitor subject closely. If symptoms recur, then no further nivolumab will be administered at that visit. Administer diphenhydramine 50 mg IV, and remain at bedside and monitor the subject until resolution of symptoms. The amount of study drug infused must be recorded on the electronic case report form (eCRF).

- For future infusions of therapy associated with infusion reaction, the following prophylactic premedications are recommended: diphenhydramine 50 mg (or equivalent) and/or acetaminophen/paracetamol 325 to 1000 mg should be administered at least 30 minutes before nivolumab infusions. If necessary, corticosteroids (up to 25 mg of Solu-Cortef or equivalent) may be used.
- For **Grade 3 or 4** symptoms: (severe reaction, Grade 3: prolonged [i.e., not rapidly responsive to symptomatic medication and/or brief interruption of infusion]; recurrence of symptoms following initial improvement; hospitalization indicated for other clinical sequelae (e.g., renal impairment, pulmonary infiltrates). Grade 4: Life-threatening; pressor or ventilatory support indicated):
  - Immediately discontinue infusion of study drug. Begin an IV infusion of normal saline and treat the subject as follows: Recommend bronchodilators, epinephrine 0.2 to 1 mg of a 1:1000 solution for subcutaneous administration or 0.1 to 0.25 mg of a 1:10,000 solution injected slowly for IV administration, and/or diphenhydramine 50 mg IV with methylprednisolone 100 mg IV (or equivalent), as needed. Subject should be monitored until the Investigator is comfortable that the symptoms will not recur. The study drug that is associated with infusion reaction will be permanently discontinued. Investigators should follow their institutional guidelines for the treatment of anaphylaxis. Remain at bedside and monitor subject until recovery of the symptoms.
  - In case of late-occurring hypersensitivity symptoms (e.g., appearance of a localized or generalized pruritus within 1 week after treatment), symptomatic treatment may be given (e.g., oral antihistamine or corticosteroids).

### 11.5 Dose Delay Criteria

Dose delay criteria apply for all drug-related events (regardless of whether or not the event is attributed to nivolumab, ipilimumab or both).

Nivolumab and ipilimumab administration should be delayed for the following:

- Any Grade  $\geq 2$  non-skin, drug-related adverse event, with the following exceptions:
  - Grade 2 drug-related fatigue or laboratory abnormalities do not require a treatment delay.
- Any Grade 3 skin, drug-related adverse event
- Any Grade 3 drug-related laboratory abnormality, with the following exceptions for lymphopenia, AST, ALT, or total bilirubin or asymptomatic amylase or lipase:
  - Grade 3 lymphopenia does not require dose delay

- If a subject has a baseline AST, ALT or total bilirubin that is within normal limits, delay dosing for drug-related Grade  $\geq 2$  toxicity
- If a subject has baseline AST, ALT, or total bilirubin within the Grade 1 toxicity range, delay dosing for drug-related Grade  $\geq 3$  toxicity
- Any Grade  $\geq 3$  drug-related amylase or lipase abnormality that is not associated with symptoms or clinical manifestations of pancreatitis does not require dose delay.
- Any adverse event, laboratory abnormality, or intercurrent illness which, in the judgment of the investigator, warrants delaying the dose of study medication.

Patients who require delay of nivolumab or ipilimumab should be re-evaluated weekly or more frequently if clinically indicated. Both drugs should be delayed until re-treatment criteria are met (per Section 11.7).

Nivolumab may be delayed until the next planned ipilimumab dose if the next ipilimumab dose is scheduled within the next 12 days. This will permit periodic ipilimumab dosing to be synchronized with nivolumab dosing.

Ipilimumab should be dosed at the specified interval regardless of any delays in intervening nivolumab doses. However, in order to maintain periodic synchronized dosing of ipilimumab and nivolumab, the dosing days of nivolumab and ipilimumab may be adjusted within the permitted +/- 5 day window, as long as consecutive nivolumab doses are given at least 12 days apart. Ipilimumab may be delayed beyond the 5 day window if needed to synchronize with the next nivolumab dose.

If an ipilimumab dose is delayed beyond 6 weeks from the prior ipilimumab dose, then subsequent ipilimumab doses should be rescheduled to maintain the 6 week interval between consecutive ipilimumab doses.

Dose delay of nivolumab which results in treatment interruption of  $> 6$  weeks or ipilimumab for  $> 12$  weeks require treatment discontinuation, with exceptions as noted in Section 13.0

#### 11.6 Dose Reduction Criteria

There will be no dose reductions for nivolumab or ipilimumab.

#### 11.7 Criteria to resume treatment

Patients may resume treatment with nivolumab when the drug-related AE(s) resolve(s) to Grade 1  $\leq$  or baseline, with the following exceptions:

- Patients may resume treatment in the presence of Grade 2 fatigue
- Patients who have not experienced a Grade 3 drug-related skin AE may resume treatment in the presence of Grade 2 skin toxicity
- Patients with baseline Grade 1 AST/ALT or total bilirubin who require dose delays for reasons other than a 2-grade shift in AST/ALT or total bilirubin may resume treatment in the presence of Grade 2 AST/ALT OR total bilirubin
- Patients with combined Grade 2 AST/ALT AND total bilirubin values meeting discontinuation parameters (Section 13.0) should have treatment permanently discontinued

- Drug-related pulmonary toxicity, diarrhea, or colitis must have resolved to baseline before treatment is resumed
- Drug-related endocrinopathies adequately controlled with only physiologic hormone replacement may resume treatment
- Subjects who received systemic corticosteroids for management of any drug-related toxicity must be off corticosteroids or have tapered down to an equivalent dose of prednisone □ 10 mg/day.
- Ipilimumab may not be resumed sooner than 6 weeks (+/- 5days) after the prior ipilimumab dose.
- In general, subjects who meet criteria to resume ipilimumab will also have met criteria to resume nivolumab, so it should be feasible to synchronize dosing of both drugs when resuming ipilimumab. In order to facilitate this, the dosing days of nivolumab and ipilimumab may be adjusted within the permitted +/- 5 day window, as long as consecutive nivolumab doses are given at least 12 days apart.
- In instances in which toxicity is felt to be exclusively related to ipilimumab, treatment with nivolumab alone may be resumed after retreatment criteria are met and after discussion with PI-Sponsor.

#### 11.8 Adverse Event

An adverse event (AE) is any untoward medical occurrence in a clinical investigation subject administered a pharmaceutical product during the course of a study and which does not necessarily have to have a causal relationship with this treatment. An adverse event can therefore be any unfavorable and unintended sign (including an abnormal laboratory finding), symptom, or disease temporally associated with the use of an investigational product, whether or not considered related to the medicinal product.

Disease signs, symptoms, and/or laboratory abnormalities already existing prior to the use of the product are not considered AEs after administration of the study product unless they reoccur after the patient has recovered from the pre-existing condition or they represent an exacerbation in intensity or frequency.

#### 11.9 Laboratory AEs

For this protocol, an abnormal laboratory value will not be assessed as an AE unless:

- The laboratory test result is clinically significant or meets the definition of an SAE
- The laboratory test result leads to interruption or discontinuation of study treatment
- Any laboratory test result requires a specific correlative therapy/therapeutic intervention.

Laboratory AEs will be reported by the clinical term rather than the laboratory term (e.g. anemia, rather than low hemoglobin).

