#### Toxicity monitoring and adverse events

Patients should be assessed for toxicity at least every 2 weeks so long as patient remains on study. Safety blood tests must be performed on the day of the study visit or within the 2 days *prior* to the study visit.

Toxicity will be evaluated in this study through the monitoring of all serious and non-serious AEs, defined and graded according to NCI CTCAE v4.0.

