### Definitions

Evaluation of best overall response: The best overall response is the best response recorded from the start of treatment until disease progression, as defined in Table 12.3.

Evaluable for toxicity: All patients who receive at least one dose of study therapy will be evaluable for toxicity which will be assessed according to CTCAE v4.0 as well as by documentation of dose delay/adjustments that are required.

Evaluable for objective response: All patients who receive at least one dose of study therapy will be included in the modified intent-to-treat analysis of efficacy. Patients who come off study for any reason prior to the first radiographic tumor assessment will be treated as having progressive disease.

Evaluable for primary/secondary objectives: In order to be considered eligible for the primary and secondary objectives described in this study, patients must receive (1) at least one dose of study therapy and remain on study until at least the first radiographic tumor assessment (week 6) or (2) at least one dose of study therapy and have clear clinical or radiographic progression prior to the planned first radiographic tumor assessment at week 6. Patients who come off study for reasons other than clinical/radiographic progression prior to the first radiographic tumor assessment will be replaced.

Progression free survival (PFS) is defined as the duration of time from beginning study therapy (C1D1) to time of progression or death, whichever occurs first. Clinical deterioration consistent with progressive disease in absence of radiographic evidence of progression (“clinical progression”) will be considered progression for purposes of determining PFS. In patients who continue on study therapy after an initial scan demonstrates progressive disease, if repeat scans confirm PD, then progression should be declared using the date of the initial scan. If repeat scans do not confirm PD, then the subject will not be considered to have progression at the initial scan. Patients who enroll but do not receive any study therapy will not be included in the PFS analysis. Patients who started a

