**Nivolumab dose discontinuation:**

- Any Grade 2 drug-related uveitis, eye pain or blurred vision that does not respond to topical therapy and does not improve to Grade 1 severity within the re-treatment period OR requires systemic treatment
- Any Grade 3 non-skin, drug-related adverse event lasting > 7 days, with the following exceptions for laboratory abnormalities, drug-related uveitis, pneumonitis, bronchospasm, hypersensitivity reactions, infusion reactions, and endocrinopathies:
  - Grade 3 drug-related uveitis, pneumonitis, bronchospasm, hypersensitivity reaction, or infusion reaction of any duration requires discontinuation
  - Grade 3 drug-related endocrinopathies adequately controlled with only physiologic hormone replacement do not require discontinuation
  - Grade 3 drug-related laboratory abnormalities do not require treatment discontinuation except:
    - Grade 3 drug-related thrombocytopenia > 7 days or associated with bleeding requires discontinuation
    - Any drug-related liver function test (LFT) abnormality that meets the following criteria requires discontinuation:
      - AST or ALT > 10x ULN
      - AST or ALT > 5-10x for > 2 weeks
      - Total bilirubin > 5x ULN
      - Concurrent AST or ALT > 3x ULN and total bilirubin > 2x ULN
- Any Grade 4 drug-related adverse event or laboratory abnormality, except for the following events which do not require discontinuation:
  - Grade 4 neutropenia ≤ 7 days
  - Grade 4 lymphopenia or leukopenia
  - Isolated Grade 4 amylase or lipase abnormalities that is not associated with symptoms or clinical manifestations of pancreatitis.
  - Isolated Grade 4 electrolyte imbalances/abnormalities that are not associated with clinical sequelae and are corrected with supplementation/appropriate management within 72 hours of their onset
  - Grade 4 drug-related endocrinopathies adequately controlled with only physiologic hormone replacement do not require discontinuation

- Any event that leads to delay in dosing lasting > 6 weeks from the previous dose requires discontinuation, with the following exceptions:
  - Dosing delays to allow for prolonged steroid tapers to manage drug-related adverse events are allowed. Tumor assessments should continue as per protocol even if dosing is delayed.
  - Dosing delays lasting > 6 weeks from the previous dose that occur for non-study-drug-related reasons may be allowed. Tumor assessments should continue as per protocol even if dosing is delayed.

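### Grade 3-4 amylase or lipase rises without pancreatitis can stay out of the safety table on an undefined judgment, and no graded laboratory summary is planned (minor)

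*Combined protocol and SAP*

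**What the plan says.** Section 11.9 sets the rule for laboratory values: "For this protocol, an abnormal laboratory value will not be assessed as an AE unless" one of the listed conditions holds. The first is "The laboratory test result is clinically significant or meets the definition of an SAE". The others are that the result leads to interruption or discontinuation of treatment, or that it calls for a specific therapy. No CTCAE grade appears in the rule, and clinical significance is not defined.

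Section 11.5 requires delay for "Any Grade 3 drug-related laboratory abnormality, with the following exceptions for lymphopenia, AST, ALT, or total bilirubin or asymptomatic amylase or lipase". Under those exceptions, a Grade 3 or higher "drug-related amylase or lipase abnormality that is not associated with symptoms or clinical manifestations of pancreatitis does not require dose delay". The lymphopenia exception is narrower: "Grade 3 lymphopenia does not require dose delay".

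In Section 13.0, Grade 3 laboratory abnormalities do not in general require discontinuation. The Grade 4 exemptions, for nivolumab and again for ipilimumab, include "Isolated Grade 4 amylase or lipase abnormalities that is not associated with symptoms or clinical manifestations of pancreatitis".

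On the output side, Section 9 states: "Toxicity will be evaluated in this study through the monitoring of all serious and non-serious AEs, defined and graded according to NCI CTCAE v4.0". The Definitions in Section 12 make every patient with at least one dose evaluable for toxicity, "which will be assessed according to CTCAE v4.0 as well as by documentation of dose delay/adjustments that are required". Section 17.1 (the paragraph on monitoring of data to ensure safety) says that adverse events, with all toxic effects of treatment included, will be tabulated and summarised by severity and causality. Section 14 describes no safety or laboratory analysis.

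**The concern.** The dosing rules and the reporting rule interact. A value that needs no dose action loses one of the objective routes into the adverse event data. If the patient also has no symptoms and gets no treatment, what is left is a judgment with no grade attached. Two patients with the same Grade 4 lipase could then be handled differently, each in line with the protocol.

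At stake is the completeness of the toxicity summary for this regimen. An unrecorded value can only lower the reported count. The protocol itself expects the abnormality to some degree: raised inflammatory blood proteins, with lipase as the example, are in the likely group of the combined-therapy risk list, and the tests are drawn throughout treatment.

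**Working it through.** The plan states no figure on this point, so there is none to reproduce. The check is a reading of the sections side by side, followed by an illustration of scale.

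**Step 1: follow one value through the rules.** Take a drug-related Grade 3 or isolated Grade 4 lipase rise, with no pancreatitis, no treatment given and the dose given on time.

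- Interruption: not required (Section 11.5, Grade 3 and higher).
- Discontinuation: not required for either drug (Section 13.0, general Grade 3 laboratory exception and the Grade 4 amylase/lipase exemption).
- Specific therapy: none, by construction.
- SAE definition: not met, unless the investigator regards it as an important medical event.
- Clinically significant: the investigator decides, with no grade to guide the decision.

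The value is therefore an adverse event only through judgment.

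**Step 2: look for another output that would show it.** Section 9 works through adverse events, as does the tabulation in Section 17.1. Documentation of dose delays (Section 12) cannot pick up a value that needs no delay. Section 12 also refers to CTCAE v4.0, but does not say whether graded values that fail Section 11.9 are counted. No worst-grade or shift table is described anywhere.

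**Step 3: check that the data exist.** The Section 10.0 calendar has amylase and lipase at screening, at day 1 of every cycle and at the final visit. A patient treated through week 12 has 1 screening draw plus 7 day-1 draws (weeks 0, 2, 4, 6, 8, 10, 12), so 8 in all. For lymphocytes, the differential is named at screening (Section 8), but the calendar says only complete blood count.

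**Step 4: scale, with assumed counts.** The documents give no rate for these events. Use n = 30 treated patients (Study Size). The toxicity denominator can slightly exceed 30, because replaced patients who had a dose still count. Exact 95% limits are the Beta(x, n-x+1) quantile at 0.025 and the Beta(x+1, n-x) quantile at 0.975. For x = 0 the upper limit is 1 - 0.025^(1/30) = 11.6%.

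| True count (assumed) | True row | Row if none is recorded |
|---|---|---|
| 1/30 | 3.3% (0.1 to 17.2) | 0/30, 0% (0 to 11.6) |
| 2/30 | 6.7% (0.8 to 22.1) | 0/30, 0% (0 to 11.6) |
| 3/30 | 10.0% (2.1 to 26.5) | 0/30, 0% (0 to 11.6) |

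**Step 5: occurrence is not omission.** With an assumed true rate p, the chance that at least one of 30 patients has such a rise is 1 - (1-p)^30:

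- p = 2%: 1 - 0.98^30 = 45%
- p = 5%: 1 - 0.95^30 = 79%
- p = 10%: 1 - 0.90^30 = 96%

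Omission needs a second unknown, the share q of such patients who are not recorded. If patients are independent, the chance of at least one omission is 1 - (1-pq)^30. With p = 10% and an assumed q of one half, pq = 0.10 × 0.5 = 0.05 and the chance is 79%, not 96%. With q = 0 it is zero.

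**The case against.** The strongest reply is that nothing in the plan is mistaken. Section 11.9 is a deliberate rule, any threshold for adverse events lowers counts, and the study is single-arm and descriptive with no safety objective, toxicity target or stopping rule. This stands, and it limits the point to a minor one. It does not remove it: Section 17.1 undertakes to cover all toxic effects, and for these values inclusion turns on an undefined judgment and not on grade.

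A second reply is that other text closes the gap. Section 11.8 counts abnormal laboratory findings among adverse events, adverse events are assessed at each dosing visit, and using the exemptions means someone has graded the value and considered pancreatitis. The investigator may also delay for any laboratory abnormality, and the value then qualifies. These make recording more likely. They do not ensure it, because Section 11.9 expressly narrows the definition for this protocol.

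A third reply is that nothing is lost, since the values are collected and can be graded later. That is true and is why the fix is cheap.

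Some stronger readings are tempting but unsupported:

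- A reader might infer that Grade 3-4 lipase rises are expected to be common. The combined-therapy list gives no grade, and the nivolumab list puts the same item under rare but serious.
- A reader might take 45%, 79% and 96% as chances of under-counting. They are chances of occurrence under assumed rates.
- A reader might extend the point to all cytopenias. Drug-related Grade 3 leukopenia is not excepted from delay in Section 11.5, and Grade 4 lymphopenia is exempt from discontinuation but not expressly from delay.

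**Conclusion.** The point holds as a minor reporting gap. For drug-related Grade 3-4 amylase or lipase rises without pancreatitis that are not delayed, treated or serious, entry into the adverse event tabulation depends only on the investigator's view of clinical significance. The planned safety summary can therefore under-count them.

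The size is unknown and may be zero. The shift of 3.3 to 10.0 percentage points in a single row rests on assumed counts of 1 to 3 in 30 and on none being recorded, which is the worst case for each count. If every case is judged significant, there is no effect.

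A reader might infer that the trial's conclusions, or a safety comparison with the earlier cohort on the same regimen, are biased. The documents do not support that. No primary or secondary objective uses toxicity, no formal comparison with that cohort is planned, and nothing shows how its laboratory events were counted. Grade 3 lymphopenia follows the same logic, but is the weaker case because on-treatment differentials are not confirmed.

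**What to change.** Keep Section 11.9 as the rule for adverse event reporting. Add to the safety summary in Section 17.1 one table for all patients with at least one dose: worst post-baseline CTCAE v4.0 grade, and shift from baseline grade, for amylase and lipase, whether or not the value was recorded as an adverse event. Add a lymphocyte row only if differentials are available on treatment.

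The cost is one extra table. Amylase and lipase need no new samples, visits or patients. The one downside is that the toxicity summary may look slightly less favourable.
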